## Research Design and Methods

### Study Participants

**Study Participants:** It is our goal to recruit 12 eligible hypotensive individuals with injuries T6 and above. We anticipate recruitment of

4-5 eligible individuals each year of the project. Individuals with SCI will be recruited from the Northern New Jersey SCI Model System database via study solicitation flyer distribution at support groups and inpatient and outpatient treatment facilities.

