### Methods & Procedures:

We aim to compare stimulation parameters (frequency and amplitude, 1-ms pulses) using a monophasic waveform for different spinal segment sites to modulate BP. Sites for stimulation during a series of seated experiments will include 1) T 7/8; 2) T 9/10; 3) T11/12; and 4) L1/2, while beat-to-beat seated BP is continuously monitored and recorded in hypotensive individuals with SCI.

This study will take approximately 7-study visits, between 1-3 hours, per subject. Participants will be asked to arrive between 8:00 am and noon at the James J Peters VA Medical Center (JJP VAMC), after a normal breakfast and a good night sleep. The participants will be asked to not drink alcohol or caffeine 12 hours prior to their visit and there will be at least 3 days between study visits.

Approach: We will compare the electrode placement sites and amplitude during seated rest to modulate BP. We anticipate that BP responses will vary among the participants regarding the location of the electrode placement site and signal amplitude. Participants will visit the laboratory 8 times: visit 1): informed consent and medical intake to determine eligibility for enrollment in the study. Visits 2-8: amplitude (mA) mapping sessions at each electrode placement site (randomized), with continuous beat-to-beat BP monitoring at the finger arteriole and at 1-minute intervals at the brachial artery.

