Amplitude Parameter Mapping Visits 2-8: Before TSCS, electrodes will be placed on the vertebral midline at the spinous process (T7/8, T9/10, T11/12, L1/2), and the active site will be randomized. Each visit, we will complete one electrode placement site. Amplitude ramping will start at 10mA, with 10mA increments (pulse width, 1ms, frequency 30 Hz as shown (13)). Continuous real-time BP and heart rate will be measured for 5-minutes, before, during and after stimulation. During ramping, amplitude will stop increasing when SBP reaches optimal SBP between 110-120 mmHg (100-120 mmHg females) or reaches 100 mA with no SBP response (see below TSCS decision Tree). Amplitude will be decreased in 10 mA decrements in stimulation. BP will be continuously recorded during the rest period. Bilateral muscle activation (rectus femoris, medial hamstring, and gastrocnemius) will be monitored during all experiments to determine if skeletal muscle contractions are contributing to increases in BP. Additionally, signs and symptoms of autonomic dysreflexia will be monitored during TSCS testing in visits 3-6 by a questionnaire (**Appendix**). After every incremental increase of amplitude, investigator will ask participant if he/she is experiencing any symptoms. Maximum ramping amplitude will be 100 mA and testing will be halted if participant experiences any discomfort during testing. Based on preliminary work, regulation of neuromodulation of BP will occur at stimulation levels less than 100mA.

Participants will be notified by investigator if any of the findings from this study will affect the participants' health or welfare.

- Cardiovascular Assessments: While the subject is seated 3 ECG electrodes will be affixed to the chest and abdomen for continuous monitoring of HR and respiration rate (RR). Brachial BP will be monitored at 1 minute intervals using a standard adult BP cuff placed at the right upper arm, and beat-to-beat finger arteriolar BP will be continuously monitored from the right

middle finger throughout testing. Mean arterial pressure (mmHg) will be calculated from brachial BP using the formula: [systolic BP + (2\* diastolic BP)]/3. Beat-to-beat HR, RR and BP data will be viewed in real-time and stored for subsequent analysis using customized programs created with LabView graphical software.

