Targeted Transcutaneous
Stimulation to Restore Autonomic
Cardiovascular Health in Veterans
with Spinal Cord Injury

NCT05180227

August 18, 2025

Statistical analysis plan:

The primary outcome variable will be systolic blood pressure. Data will be analyzed with a mixed-modeling approach to determine which stimulation parameters consistently yield increases in systolic blood pressure. Participant will be modeled as a random effect and stimulation characteristics as fixed effects including: cathodal stimulation site (T7/8, T9/10, T11/12, and L1/2); stimulation frequency (30, 60, 120 Hz); waveform (monophasic, biphasic, asymmetric biphasic); pulse width (40 - 1000 μ s); carrier frequency (0, 10kHz); and stimulation current (0–120mA). To quantify the effect size of each participant's optimal tSCS parameters, each participant's blood pressure response will be compared to baseline blood pressure to calculate Cohen's d and confidence intervals. All analyses will be performed using R software. The lme4 package will be used to perform the mixed-models analyses for the ratio-scale data. The ordinal package in R will be used to analyze the Likert-scale-type data. The 95% level of confidence will be used. We used the R software simr package for multi-level models for power calculations with fixed effects variables of waveform and electrode site. Given the number of repeated measurements of SBP in each participant, we anticipate having *95% power to detect <2-mm-Hg mean differences at the 95% level of confidence.

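### Sites are tested one per visit in random order with no stated balancing and no visit term in the model, so any trend across visits adds avoidable noise to the pooled site contrasts

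*Protocol*

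**What the plan says.** - **Allocation.** Protocol, Amplitude Parameter Mapping Visits 2-8: "Each visit, we will complete one electrode placement site", and "the active site will be randomized". Neither this paragraph nor the general Methods & Procedures text names sequences, blocks or any form of Latin square.
- **Sample size.** Protocol, Study Participants: "It is our goal to recruit 12 eligible hypotensive individuals with injuries T6 and above". This is a target, and no dropout allowance is given.
- **Visits.** Protocol, Methods & Procedures: "Visits 2-8: amplitude (mA) mapping sessions at each electrode placement site (randomized". That is seven mapping visits for four sites. The mapping paragraph says that dysreflexia symptoms "will be monitored during TSCS testing in visits 3-6 by a questionnaire", which is four visits.
- **Model.** SAP: "Participant will be modeled as a random effect and stimulation characteristics as fixed effects including" site, frequency, waveform, pulse width, carrier frequency and current. No visit, period, order or carry-over effect appears. The outcome is systolic pressure itself. Baseline is mentioned only for each participant's Cohen's d at the optimal setting.
- **Power.** The SAP claims 95% power for mean differences below 2 mmHg. It gives no SD and no number of measurements.

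**The concern.** Within a participant, each site is tied to a visit. Readings may drift over visits through habituation, falling anxiety or a lasting effect of earlier stimulation. A site that happens to be tested late more often than another would then carry part of that drift. Nothing stated in the design or the model removes it.

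The pooled site contrast matters because the protocol's first hypothesis names T7/8 as the optimal placement. The SAP also claims to resolve differences of under 2 mmHg, so an extra error of around 1 mmHg would count if that claim is right.

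**Working it through.** **Inputs.** 12 participants, four sites and one site per visit (protocol); 95% power at 2 mmHg and 95% confidence (SAP, taken as two-sided). The visit trend is an assumption, shown from 0 to 2 mmHg per visit.

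**1. The plan's own figure.** The 95% power cannot be reproduced or refuted, because no SD or number of measurements is given. It can be back-solved. The implied standard error of a site contrast is 2/(1.960 + 1.645) = 0.555 mmHg. With n = 12, the implied SD of a within-participant site difference is 0.555 × √12 = 1.92 mmHg (normal approximation; 1.75 with t on 11 df). The residual SD per visit is 1.92/√2 = 1.36 mmHg.

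**2. Imbalance under independent random orders.** For K visit slots, the difference in position between two sites has variance K(K+1)/6.

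- K = 4: 20/6 = 3.33. The SD of the mean over 12 participants is √(3.33/12) = 0.53 visits.
- In simulated allocations, a given pair of sites differed by at least half a visit in 39% of draws and by at least one visit in 7%.
- Perfect balance at the first visit has probability 12!/(3!⁴ × 4¹²) = 2.2%.
- If the four sites fell at random over seven slots, the SD would be √((56/6)/12) = 0.88 visits.

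**3. Added error.** Extra SD = trend × 0.527: 0 mmHg at no trend, 0.53 at 1 mmHg per visit, 1.05 at 2 mmHg per visit.

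**4. How much that matters depends on the underlying SD.**

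| SD of site difference (mmHg) | SE, no trend | SE, 1 mmHg/visit | SE, 2 mmHg/visit |
|---|---|---|---|
| 1.92 (implied by the SAP) | 0.555 | √(0.308 + 0.278) = 0.77 (+38%) | √(0.308 + 1.111) = 1.19 (+115%) |
| 5 (assumed) | 1.44 | √(2.083 + 0.278) = 1.54 (+6%) | √(2.083 + 1.111) = 1.79 (+24%) |
| 10 (assumed) | 2.89 | √(8.333 + 0.278) = 2.93 (+1.7%) | √(8.333 + 1.111) = 3.07 (+6%) |

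**5. Which remedy does the work.** The simulation used 12 participants × 4 visits, participant and site effects, residual SD 1.36, a true difference of 2 mmHg and 3,000 runs per cell. Entries are the empirical SD of the contrast in mmHg, then power.

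| Trend (mmHg/visit) | Random order, no visit term | Random order + visit term | Williams square, no visit term | Williams square + visit term |
|---|---|---|---|---|
| 0 | 0.55; 94.5% | 0.59; 91.0% | 0.57; 93.5% | 0.56; 93.6% |
| 0.5 | 0.62; 88.1% | 0.58; 91.9% | 0.55; 90.1% | 0.55; 93.8% |
| 1 | 0.78; 71.4% | 0.58; 90.3% | 0.55; 76.5% | 0.55; 93.4% |
| 2 | 1.18; 37.4% | 0.58; 90.7% | 0.55; 19.3% | 0.56; 93.9% |

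Under random order without the term, the estimate stayed centred on 2 mmHg and type I error was 4.6% to 5.3%. The square without the term estimates the contrast precisely, but the model does not know it. Its reported SE averages 0.78 at 1 mmHg per visit and 1.23 at 2, so power is lost anyway.

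**The case against.** **The lack of balance is inferred from silence.** This stands. The protocol gives no method of randomisation, and the SAP introduces its list of fixed effects in a way that may leave it open. If balance or a visit effect is already intended, writing it down settles the point.

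**Readers might infer bias or confounding of site with visit.** The documents do not support that for the pooled contrast. Order is randomised, so the estimates stay centred and the type I error is nominal. The loss is precision.

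**Readers might also infer that 12 participants fit a four-period square exactly.** That is not established. The protocol gives seven mapping visits for four sites and describes 12 as a goal. The SAP adds frequencies, waveforms and carriers without assigning them to visits.

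**The size rests on an unsupported trend and an unverified SD.** This also stands, which is why the range is shown. With an SD of 5 or 10 mmHg, a trend of 1 mmHg per visit changes little.

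**Existing safeguards reduce drift.** Visits are spaced by three days or more, arrival time and food and drink are standardised, and pressure is recorded before stimulation at each visit. These help. If the analysis used change from each visit's own baseline, additive drift in level would cancel and only drift in the response would remain. The SAP does not say that its model does so.

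**The stated objective is an individual map.** Correct, and it limits the benefit. If each site is tested once, site and visit stay confounded within a participant under any square.

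**Conclusion.** The point holds as a modest, inexpensive improvement to the group-level site comparison. As written, neither the allocation nor the model removes a visit trend. Such a trend would add an error SD of 0.53 mmHg to each pooled site contrast for every 1 mmHg per visit, assuming independent random orders over four visits and 12 completers.

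On the SD implied by the SAP's power statement, analytic power for 2 mmHg would fall from 95% to about 74% at 1 mmHg per visit and 39% at 2. On an SD of 5 to 10 mmHg, the cost at 1 mmHg per visit is a standard error about 6% or under 2% larger. With no trend there is no loss. The documents do not show which case applies, and these figures do not refute the power claim.

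**What to change.** In order of importance:

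1. **Add visit order as a categorical fixed effect in the mixed model.** The cost is 3 df with four site visits. Under random order with no trend, simulated power falls from 94.5% to 91.0%; with any trend tested it stays at 90% to 92%. This can still be done if enrolment has begun.
2. **Reconcile the visit schedule.** Mapping is placed in visits 2 to 8, yet there are four sites at one per visit, and dysreflexia monitoring covers visits 3 to 6. Say what each visit contains and how the SAP's other stimulation settings map to visits. The cost is drafting only.
3. **For participants not yet allocated, assign the four site visits from a four-sequence Latin or Williams square**, three per sequence if 12 are enrolled. Any Latin square balances site over visit; the Williams form also balances the preceding site. The cost is a new randomisation list and a rule for dropouts, such as giving a replacement the same sequence. Keep the visit term, because the square alone leaves the reported standard error inflated.

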# **Targeted Transcutaneous Spinal Cord Stimulation to Restore Autonomic Cardiovascular Health in Individuals with Spinal Cord Injury**

## **Abstract:**

Recent evidence indicates that increased arterial stiffness is an independent predictor of cardiovascular disease risk, which may contribute to the heightened cardiovascular morbidity and mortality in the spinal cord injury (SCI), compared to general, population. Increased reliance on the renin-angiotensin-aldosterone system (RAAS) is believed to mitigate orthostatic falls in blood pressure (BP) and reduce the severity of symptoms reporting; however, findings in the general population link the RAAS with vascular restructuring and remodeling. Therefore, clinical intervention to stabilize and normalize BP should be a priority in hypotensive individuals with SCI. Advances in methods of neuromodulation of the spinal processes offer a non-pharmacologic approach to restore endogenous autonomic cardiovascular control and improve orthostatic BP control. Based on our present understanding of the somatovisceral integration within the spinal cord, it is plausible that transcutaneous spinal cord stimulation (TSCS) can be targeted to excite and modulate appropriate spinal autonomic circuitry to rapidly normalize orthostatic BP; however, electrode placement and stimulation parameter mapping is needed to optimize orthostatic BP control. Therefore, our primary aim is to identify an individualized map using noninvasive TSCS of the spinal autonomic circuitry that results in an increase of seated BP. Our secondary aim is to compare BP, cerebral blood flow velocity (CBFv), plasma concentrations of norepinephrine, renin and aldosterone during a head-up tilt with and without optimal TSCS. Participants will go through a screening process to determine if participant experiences orthostatic hypotension. 12 participants who are cleared, will go through multiple mapping sessions to find out the most appropriate electrode placement to increase BP and then will perform an orthostatic provocation on a tilt table during stimulation to determine differences with stim and without.

**Objective:** To identify an individualized map of the spinal autonomic circuitry that results in an increase of seated BP using noninvasive TSCS.

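### No repeat session at a site is stated and the visit counts conflict, so a participant's own best site may not be separable from session-to-session variation

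*Protocol*

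**What the plan says.** The Protocol's Abstract states that "our primary aim is to identify an individualized map using noninvasive TSCS", and the Objective repeats it: "To identify an individualized map of the spinal autonomic circuitry that results in an increase of seated BP using noninvasive TSCS". The sample is 12 participants (Study Participants). The sites are "1) T 7/8; 2) T 9/10; 3) T11/12; and 4) L1/2" (Methods & Procedures).

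On scheduling, the section Amplitude Parameter Mapping Visits 2-8 says "Each visit, we will complete one electrode placement site". Methods & Procedures requires at least three days between visits. No section mentions a second session at a site, or a session that confirms a chosen site against the others.

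The visit counts do not agree:
- The Approach paragraph lists "Visits 2-8: amplitude (mA) mapping sessions at each electrode placement site (randomized", which is seven visits for four sites.
- The mapping section says that autonomic dysreflexia "will be monitored during TSCS testing in visits 3-6 by a questionnaire", which is four visits for four sites.
- Totals are given as about 7 and as 8 (Methods & Procedures) and as 9 (Study Compensation).
- The tilt test with stimulation has no visit number.

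In the SAP, "Participant will be modeled as a random effect" and the stimulation characteristics, site included, are fixed effects. No session term and no participant-by-site term is named. Each participant's optimal setting is compared with that participant's baseline, not with the other sites.

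**The concern.** With one site per visit and days between visits, every within-person comparison of sites is also a comparison of days. If a site is visited once, a person who truly responds better at T9/10 looks the same as a person who had a more responsive day when T9/10 was tested.

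The SAP model does not address this. With a participant intercept and fixed site effects, the fitted site ranking is the same for all 12 participants, so the model cannot express an individual map. It also treats repeated readings from one session as independent once participant and the fixed effects are accounted for, although they share that day's response.

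At stake is the primary claim. The trial could report up to 12 personal maps and carry each person's chosen setting into the stimulated tilt, without evidence that the same site would be chosen again. A site ranking common to the group could be read as individual variation.

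**Working it through.** **1. The plan's own figure.** The SAP states 95% power for mean differences below 2 mmHg. It gives no SD, variance components or number of readings, so the figure cannot be rebuilt; it can only be back-solved.
- Taking one session per site, n = 12 and a two-sided 5% paired t test, 95% power for 2 mmHg needs a paired-difference SD of at most 1.75 mmHg. That is a session SD of 1.75/√2 ≈ 1.2 mmHg.
- At session SDs of 3, 5 and 8 mmHg, the same test has power of 32%, 15% and 9%.
- If every reading counts as independent, the figure is reached with about 14, 35 or 54 readings per participant per site, at reading SDs of 5, 8 or 10 mmHg.

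So the stated power is easy to reach when the session level is ignored and hard to reach when it is not. It says nothing about individual maps.

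**2. Identifiability (no SD needed).** Participant-by-site has (12 − 1) × (4 − 1) = 33 df. Replicate df for session variance are sessions minus participant-site cells.
- One session per site: 48 − 48 = 0.
- Seven mapping sessions (three sites twice, one once): 12 × 7 − 48 = 36.

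With 0 df, no analysis can split preference from session variation.

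**3. Readings within a session do not replace sessions.** Suppose there is no participant-by-site effect, m readings per session, and q is the ratio of session SD to reading SD. A participant-by-site F test that uses readings as error has its statistic inflated by 1 + m·q². For m = 10 and q = 0.5 this is 1 + 10 × 0.25 = 3.5. The critical value on 33 and 432 df is 1.46, so the false-positive rate is P(F > 1.46/3.5) = 99.8%. For q = 0.25 the factor is 1.625 and the rate is 63%.

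**4. How often could false individuality appear?** Assume that all participants share one best site, better than the other three by δ, with session SD σ and one session per site. Then the share mis-mapped is 1 − ∫ φ(z) Φ(z + δ/σ)³ dz, which depends only on δ/σ. Simulated results:

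| δ (mmHg) | σ (mmHg) | mis-mapped |
|---|---|---|
| 3 | 4 to 8 | 53% to 64% |
| 5 | 4 to 8 | 37% to 57% |
| 5 | 2 | 9% |
| 10 | 5 | 18% |
| 10 | 3 | 2.5% |
| 10 | 2 | 0.1% |

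At δ = 5 and σ = 5, 45% are mis-mapped and the 12 participants show on average 3.6 different best sites. All δ and σ here are assumptions, because the documents give no session SD of response.

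**5. What repeats would buy.** With three randomly chosen sites repeated per participant, the participant-by-site test has 33 and 36 df (critical value 1.76). Simulated power is 0.73 at a participant-by-site SD of 5 and session SD of 6. Over SDs of 3-8 and 4-8 it runs from 0.15 to 1.00, with size about 0.05 when there is no effect.

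**The case against.** Five arguments weigh against the concern.

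1. A reader might infer that the plan gives exactly one session per site. The documents do not say so: one site per visit is not one visit per site. Read literally, seven mapping visits over four sites force at least three repeats. Visits 3-6 point the other way. This stands, and it makes the confounding conditional.

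2. A reader might also infer that the maps would look individual whatever the truth. That is not supported either. When the shared advantage is large against session noise, nearly everyone is mapped to the shared site, and the decision tree's 10 mmHg response threshold suggests that advantages of that size are not far-fetched. This stands, although without replication the trial could not tell which case it is in.

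3. The simulation picks the site with the highest mean SBP, whereas the protocol stops the ramp once SBP reaches a target band. Successful sites may end at similar SBP and differ in current reached. This stands, so the percentages are illustrative only. It does not touch the count of replicate df.

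4. The baseline taken in the same session removes day-to-day shifts in resting pressure. True, but day-to-day variation in the response to stimulation remains.

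5. The aim can be read as finding a setting that works for each person, and neither hypothesis tests whether people differ. That weakens any claim that individuality is formally tested. The word individualized is still in the primary aim, and the SAP still refers to each participant's optimal parameters.

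**Conclusion.** The point holds in conditional form. The primary aim is individual, no repeat session is stated, the visit counts conflict, and the SAP names neither a session term nor a participant-by-site term. If each site has one session, personal preference and session variation cannot be separated; that rests on the df count alone. If the seven listed mapping visits include repeats, separation is possible (36 df), but the model as written would not use them.

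How often shared preference would pass for individual preference depends on δ/σ, which the documents do not supply. It is 37-64% for 3-5 mmHg and session SD of 4-8, and under 3% for 10 mmHg and session SD of 3 or less, ignoring the stop-at-target ramp. The change is worth making because it determines what can be concluded about the primary aim.

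**What to change.** - **Schedule.** Reconcile the visit passages (mapping in visits 2-8 against testing in visits 3-6; totals of about 7, 8 and 9; the unnumbered stimulated tilt) and state the number of sessions per site.
- **Repeats.** If visits 2-8 are all mapping visits, use the three beyond the four sites to repeat sites drawn at random for each participant. The documents do not establish that these visits are free: the tilt or the SAP's other frequencies and waveforms may need them.
- **Model.** Add random terms for participant-by-site and for session (participant-by-visit). With single sessions the two merge into one term, which should still be included so that readings from one session are not treated as independent.
- **Reporting.** Give each participant's site as a shrunken, model-predicted estimate with an interval. Do not require a significant contrast with the runner-up site. With three repeats and a 95% criterion, about 1% of participants would meet that rule at a participant-by-site SD of 5 and session SD of 6, and 0-24% over SDs of 3-8 and 4-8.
- **If there are no repeats.** Label the individual maps exploratory and rest the conclusion on the group-level site comparison.

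The cost is wording in the protocol and SAP, plus either three visits no longer available for other settings or a more modest individual claim.

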## **Hypotheses:**

1. We hypothesize that electrode placement at the lower thoracic (T7/8) and 50 mA current will be the optimal parameters to increase cardiovascular function.
2. We hypothesize that seated systolic BP will significantly increase following optimal TSCS.

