Mounting evidence supports the targeted use of electrical stimulation of the spinal cord to modulate autonomic nervous system circuitry and promote restoration of orthostatic BP control (44-47). To date, there is only one recent paper describing the effects of non-invasive transcutaneous spinal cord stimulation (TSCS) to increase BP during an orthostatic provocation. The TSCS parameters included electrode placement at the thoracic-7/8 vertebral level, using 10-70 mA current at 30 Hz, with monophasic, 1-ms pulses and the results demonstrated increases in orthostatic BP, improved cardiac contractility, and increased CBFv during active stimulation in 5 individuals with motor complete SCI (48). However, the investigators used TSCS at only one electrode placement site, and did not provide rationale for the electrode placement site, the frequency or pulse width chosen (48). The authors noted quiet electromyography (EMG) recordings of the lower-limb during stimulation, and conclude that the BP response were not attributed to the skeletal muscle pump action (48). The increase in orthostatic BP were therefore ascribed to excitation of sympathetic pre-ganglionic neurons leading to vasoconstriction and they conclude that TSCS may be a viable therapy for restoring autonomic cardiovascular control after SCI (48). However, we need to understand the effects of varied electrode placement site, and stimulation parameters (Hz, mA, pulse width) on BP and autonomic function before wide spread utility of TSCS can be recommended for clinical intervention.

[figure not shown]

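### Muscle activity is recorded only in the legs while current is applied over the trunk, so quiet recordings cannot exclude a trunk-muscle contribution to the blood pressure rise

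*Protocol*

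**What the plan says.** In the Protocol's Methods & Procedures, the paragraph on amplitude mapping (Visits 2-8) says: "Bilateral muscle activation (rectus femoris, medial hamstring, and gastrocnemius) will be monitored during all experiments to determine if skeletal muscle contractions are contributing". The contribution meant is to a rise in blood pressure. The purpose is stated for skeletal muscle in general and is not confined to the legs.

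The same paragraph gives the stimulation sites: "electrodes will be placed on the vertebral midline at the spinous process (T7/8, T9/10, T11/12, L1/2". On intensity it says: "Maximum ramping amplitude will be 100 mA and testing will be halted if participant experiences any discomfort during testing". The SAP's range for current runs from 0 to 120 mA.

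The only other electrodes described on the trunk are for cardiac and respiratory monitoring: "3 ECG electrodes will be affixed to the chest and abdomen for continuous monitoring of HR and respiration rate (RR".

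The Review of Literature describes one earlier study of transcutaneous stimulation during an orthostatic challenge. "The authors noted quiet electromyography (EMG) recordings of the lower-limb during stimulation", the Protocol reports, and those authors "conclude that the BP response were not attributed to the skeletal muscle pump action". The rise was then "ascribed to excitation of sympathetic pre-ganglionic neurons leading to vasoconstriction".

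Under Hypotheses, the sponsor expects that "electrode placement at the lower thoracic (T7/8) and 50 mA current will be the optimal parameters".

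**The concern.** The recording does not match the question it is meant to answer. The Objective is an individualized map of spinal autonomic circuitry, so whether a pressure rise is autonomic or muscular bears on what the map means. If trunk muscle contracts under the electrode and that contraction raises SBP, leg recordings could stay quiet while the rise is partly muscular.

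The earlier study shows how the inference can be made: quiet legs, therefore no muscle pump, therefore sympathetic excitation. The Protocol criticises that study for using a single site and for not justifying its site, frequency and pulse width. It does not comment on the leg-only recording, and it plans leg-only recording itself.

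At stake is the attribution of mechanism. The SBP measurements are not in question.

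**Working it through.** No formula tests this point, and the plan gives no figure to reproduce. The check sets the relevant places side by side.

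**1. What is recorded against where current is applied**

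| Item | Source | Count |
|---|---|---|
| Monitored muscles in the leg | Protocol, Amplitude Parameter Mapping | 3 of 3 |
| Monitored muscles in the trunk | same | 0 of 3 |
| Stimulation sites over the trunk | same | 4 of 4 |
| Muscle-activity terms in the model | SAP | 0 |

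The ECG electrodes on the chest and abdomen serve heart rate and respiration, and no muscle measure is derived from them. The mapping paragraph does not name electromyography; the term appears only in the Review of Literature. The appendix and the figures are not in the text available for review.

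**2. Whether anything else would reveal trunk contraction**

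- Participants are asked about symptoms after each step in current. All have injuries at or above T6 and are graded A, B or C (Inclusion Criteria), so every stimulation site is below the lesion, where sensation may be impaired. A symptom question is not a measure of muscle activity.
- Staff might see a contraction, but no such observation is planned as data.
- Risk and Discomforts lists contractures and muscle tears among the possible effects of stimulation and does not confine them to the legs. The Protocol thus foresees muscle effects in general.

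**3. Whether muscle activity enters site selection or analysis**

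- The decision tree ramps and stops on SBP, tolerability and current.
- The SAP's fixed effects are site, frequency, waveform, pulse width, carrier frequency and current.
- Neither uses muscle activity, so where it is recorded cannot move the SBP-based ranking of sites.

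**4. Whether trunk recording is practicable**

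Clear interval between pulses = 1000 / frequency − pulse width, in ms, with the 1-ms pulse:

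- 30 Hz (Protocol, mapping): 33.3 − 1 = 32.3 ms
- 60 Hz (SAP): 16.7 − 1 = 15.7 ms
- 120 Hz (SAP): 8.3 − 1 = 7.3 ms

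These are upper limits on the usable window, because amplifier recovery takes part of it. The SAP also lists a 10 kHz carrier, which may add artefact of its own. Trunk channels look feasible at the Protocol's 30 Hz and may be unreadable in parts of the SAP's range.

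**The case against.** The strongest reply is that the endpoint is SBP. The hypotheses and the SAP ask which parameters raise it, and a rise is a valid observation whatever its route. This stands, and it confines the point to mechanism.

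A reader might go further and infer that the map is biased towards T7/8, the site the sponsor favours, because a muscle contribution would be visible at L1/2 and hidden at T7/8. The documents do not support that. Such a bias needs a rule that discounts a site when muscle activity is seen, and neither the decision tree nor the SAP has one. If trunk contraction raises SBP, it does so with or without trunk electrodes.

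A reader might also set a hypothetical few mmHg of muscular effect against the SAP's claimed power for differences below 2 mmHg and conclude that the ranking could turn on it. No document gives any size for such an effect, and the SAP figure is a statement about power for mean differences.

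It is fair to add that the Protocol states no rule for reading quiet muscle recordings. The autonomic inference is the earlier study's, so one can say only that it could be repeated here.

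The Abstract also plans norepinephrine, renin and aldosterone during tilt with and without optimal stimulation, so muscle recording is not the only evidence on mechanism. That stands for the tilt. No blood draw is described for the seated mapping visits, where the site is chosen.

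Finally, the physiology is largely external. The Review of Literature says that the splanchnic bed holds most of the blood volume, but not that abdominal contraction would expel it. This is accepted and carried as an assumption.

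**Conclusion.** The point holds as a mismatch between a measurement and its stated purpose. Leg recordings can support a statement about leg muscle. They cannot show that skeletal muscle in general made no contribution when all four stimulation sites are over the trunk and no trunk muscle is recorded.

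The consequence is limited: an SBP rise could be attributed to autonomic circuitry on insufficient evidence. The SBP outcome and the site ranking based on it are unaffected. The size of any trunk-muscle contribution is unknown and may be nil. The conclusion assumes, from general anatomy and physiology, that trunk muscle near the electrodes may contract and that this may raise SBP. This is a cheap improvement to the plan and not a fault in its primary analysis.

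**What to change.** **Protocol, Amplitude Parameter Mapping.** Keep the three leg muscles. Add a bilateral abdominal-wall surface pair, plus a paraspinal channel placed away from the stimulating electrode where the signal is readable, at each mapping visit and at the stimulated tilt.

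**SAP.** Define what counts as detected activity. Pre-specify a sensitivity summary of SBP response by site and current, with and without detected leg or trunk activity. With 12 participants some cells will be sparse, and muscle activity is itself a possible consequence of stimulation, so the summary should be descriptive and not an adjustment of the main model.

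**If trunk recording is not added or is unreadable.** Limit the conclusion to *no leg-muscle contraction detected*, and do not use the muscle recordings to support an autonomic mechanism. This costs only a change of wording.

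**Cost of the full change.** A few more surface electrodes per visit, a short addition to the SAP, and the handling of stimulation artefact on the trunk channels. The artefact is manageable in principle at 30 Hz, harder at 120 Hz, and uncertain with the carrier frequency.
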